1.15 Use of tissue samples in future research

No human tissue will be stored for future research. All stored data related to this study, including images and databases, will be destroyed after 10 years in compliance with the Hull

[figure not shown]
1.16 Appendix 1: Evaluating the role of diagnostic ultrasound in prostate cancer – Current clinical pathway. Referral to diagnosis

[figure not shown]
1.17 Appendix 2: Evaluating the role of diagnostic ultrasound in prostate cancer – Phase 1 recruitment

[figure not shown]
1.18 Appendix 3: Evaluating the role of diagnostic ultrasound in prostate cancer – Phase 2 recruitment

1.19 Appendix 4: Ultrasound in prostate cancer – Phase 1 Image review pathway

1.20 Appendix 5: Diagnostic ultrasound in prostate cancer – Phase 2 Image review pathway

1.21 Appendix 6: Data collection form – Standard Ultrasound

Appendix 6: Data Collection form- Standard Ultrasound

ERUP Study Data Collection Form

Lead Researcher only	Participant number:	
	Phase 1	Phase 2

Reviewer: Please circle 1 2 3 4 5 6

Date of Review:

Imaging Reviewed:

Standard US	Date of Scan
-------------	--------------

Cine Loop Images

Please indicate findings of both longitudinal sweep and transverse sweep:

Longitudinal Sweep	Findings:	Transverse Sweep	Findings:
Opinion of prostate on review of cine loop	No apparent abnormality	Opinion of prostate on review of cine loop	No apparent abnormality
	Uncertain		Uncertain
	Normal BPH nodule (s)		Normal BPH nodule (s)
	Atypical focal area (s)		Atypical focal area (s)
If lesion identified, please indicate approximate site	Rt Lateral	If lesion identified, please indicate approximate site	Right Base
	Rt Mid		Left Base
	Central/midline		Right Mid
	Lt Mid		Left Mid
	Lt Lateral		Right Apex
			Left Apex

Approximate Prostate Volume:	
Length (cm)	
Height (cm)	
Width (cm)	
Volume:	x 0.53

Unable to calculate? State reason:

1.22 Appendix 7 – Data collection form – Micro-ultrasound

Appendix 7: Data Collection form- Micro Ultrasound

ERUP Study Data Collection Form

	Phase 1	Phase 2

Reviewer: Please circle 1 2 3 4 5 6

Date of Review:

Imaging Reviewed:

Micro US	Date of Scan
----------	--------------

Cine Loop Images

Please indicate findings of both longitudinal sweep and transverse sweep:

Longitudinal Sweep	Findings:	Transverse Sweep	Findings:
Opinion of prostate on review of cine loop	No apparent abnormality	Opinion of prostate on review of cine loop	No apparent abnormality
	Uncertain		Uncertain
	Normal BPH nodule (s)		Normal BPH nodule (s)
	Atypical focal area (s)		Atypical focal area (s)
If lesion identified, please indicate approximate site	Rt Lateral	If lesion identified, please indicate approximate site	Right Base
	Rt Mid		Left Base
	Central/midline		Right Mid
	Lt Mid		Left Mid
	Lt Lateral		Right Apex
			Left Apex

Approximate Prostate Volume:	
Length (cm)	
Height (cm)	
Width (cm)	
Volume:	x 0.53

Unable to calculate? State reason:

1.23 Appendix 8 – Phase 3 Implementation Survey

Appendix 8 – Phase 3 Implementation Survey

Evaluating the Role of Ultrasound in Prostate Cancer Study (ERUP Study)

Implementation of new technology into clinical practice survey

This survey is designed to help get a better understanding of how to apply and integrate new technologies and complex interventions in health care.

This survey asks questions about the implementation of micro-ultrasound in prostate imaging. We understand that people involved with prostate imaging have different roles, and that people may have more than one role.

From the statements below please choose an option that best describes *your main role* in relation to micro-ultrasound in prostate cancer assessment:

- I am, or will be, involved in managing micro-US in prostate assessment
- I am, or will be, involved in performing micro-US and prostate imaging
- I am, or will be, involved in the interpretation of micro-US as radiologist or at MDT

For this survey, please answer all the statements from the perspective of the role you specify. Depending on your role or responsibilities in relation to micro-ultrasound, some statements may be more relevant than others.

The survey is in 3 parts. Part A asks some brief questions about yourself and your role. Part B includes three general questions about micro-ultrasound and prostate imaging; Part C contains a set of more detailed questions about micro-ultrasound and prostate cancer assessment. For each statement in Part C, there is the option to agree or disagree with what is being asked (OPTION A). However, if you feel that the statement is not relevant to you, there are also options to tell us why (OPTION B).

Please take the time to decide which answer best suits your experience for each statement and tick the appropriate box

Part A: About Yourself

Question 1:

Please provide your professional background:

Sonographer	
Consultant Radiologist	
Radiology Registrar	
Consultant Urologist	
Urology Registrar	
Would rather not say	

References

- Da Silva, V., I. Cagiannos, L. T. Lavallée, R. Mallick, K. Witiuk, S. Cnossen, J. A. Eastham, D. A. Fergusson, C. Morash & R. H. Breau (2017) An assessment of Prostate Cancer Research International: Active Surveillance (PRIAS) criteria for active surveillance of clinically low-risk prostate cancer patients. *Canadian Urological Association Journal*, 11, 238.

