Participants in phase 3 will then be provided with training using specific multi-parametric US techniques and will regularly score multi-parametric US examinations. Participants' confidence in knowledge and skills, related to prostate cancer evaluation using US, and how they feel this can be implemented into regular patient care will be assessed, using the same adapted survey at baseline at 6 - 12 months' post implementation.

1.4.4 Phase 4:

A fourth phase of the study is planned. Once outcomes from the initial 3 phases of the study are known the lead researcher intends to organise a national meeting where results will be presented and discussion held between the research team and other centres providing a diagnostic prostate cancer service. The aim of this event is to disseminate results and to obtain a wider understanding of

its acceptance beyond local practice. Multi-parametric ultrasound is novel and there may be resistance to wider implementation. Opportunities and barriers will be explored at this phase 4 event.

The study phases will run concurrently and will be managed by the lead researcher.

1.5 Study design and methodology – Phase 1

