1.7.2.2 NPT domains

The survey will investigate the four domains of NPT. It will investigate the ways that participants make sense of the work of implementing and integrating multi-parametric and micro ultrasound into practice (coherence); how they engage with it (cognitive participation); enact it (collective action); and appraise its effects (reflexive monitoring). This phase of the study will evaluate any differences between different grades of staff using ultrasound in this study and between professional groups involved. Skill mix is an important consideration when implementing new techniques or interventions to ensure that these can be successfully integrated into real world clinical practice.

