1.7.11 Data analysis

A narrative of the qualitative data collected will be produced to identify the main themes that may provide an opportunity for development or either technology or skill set of the participant as well as identifying the barriers to implementation.

1.8 Phase 4

A fourth phase of the study is planned. Once outcomes from the initial 3 phases of the study are known the lead researcher intends to participate in a national meeting where results will be presented and discussion held between the research team and other centres providing a diagnostic prostate cancer service. The lead researcher has experience of planning and organising national study events and has access to the British Medical Ultrasound (BMUS) Team who will facilitate. The event will be open to all centres providing a prostate service. Notes will be taken during the event to form a narrative of proposed service developments. Attendees at the event will be informed that the event is being undertaken as an outcome of the research study and will be invited to participate in discussions around the study findings and implications for future service delivery.

1.8.1 Inclusion criteria for phase 4

- Delegates attending the specific prostate imaging workshop organised through BMUS
- Able to provide informed consent to the study
- Delegates who are happy to participate in discussion but who do not want their own comments recorded. Reference is made to the Phase 4 consent to study sheet (ICF V2 03.11.2021)

1.8.2 Exclusion criteria for phase 4

- Delegates attending the study event who do not consent to participate in the study

- Delegates who register for the study event but fail to attend. Notes from face to face discussion only will be recorded in the interests of transparency for all participants

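### The phase 3 survey is worded for micro-ultrasound only, while phase 3 is meant to assess implementation of multi-parametric and micro ultrasound

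*Protocol*

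**What the plan says.** **The survey (Appendix 8).** The introduction states the subject: "This survey asks questions about the implementation of micro-ultrasound in prostate imaging". Respondents then choose their main role from three options, and each option refers to micro-US. The three parts are described next. Part A concerns the respondent. For the other two: "Part B includes three general questions about micro-ultrasound and prostate imaging" and "Part C contains a set of more detailed questions about micro-ultrasound and prostate cancer assessment".

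**The scope of phase 3.** Section 1.4.3 says the survey is to show whether and how the new, complex multi-parametric techniques can be put into routine use. Section 1.7 gives the aim as staff views on the novel use of both multi-parametric and micro ultrasound. Section 1.7.2.2 says the four domains of Normalisation Process Theory will be explored for "implementing and integrating multi-parametric and micro ultrasound into practice". Section 1.1.2 defines the multi-parametric assessment as standard-frequency, Doppler and high-frequency ultrasound, the last being micro-ultrasound.

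**Other tasks given to the same survey.** Section 1.4.3.1 says it will assess participants' "confidence in knowledge and skills, related to prostate cancer evaluation using US", at baseline and again 6 to 12 months later. Section 1.7.11 adds: "A narrative of the qualitative data collected will be produced to identify the main themes".

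**The concern.** A survey measures what its questions ask about. If respondents are told that the subject is micro-ultrasound, and the item blocks are described as being about micro-ultrasound, their answers are about that probe. They do not show whether staff find diagnostic use of standard-frequency or Doppler imaging coherent, workable or worth adopting.

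This matters because sonographers may regard these techniques quite differently. The micro-ultrasound machine is new equipment, the first installed in the UK according to section 1.10.3.3. Standard transrectal ultrasound is familiar as a biopsy guide but not as a diagnostic test. A favourable or unfavourable answer about one need not carry over to the other. If phase 3 is reported under its stated aim, conclusions about multi-parametric ultrasound would rest on questions about one component of it.

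The timing leaves little room for repair. The survey is given at the start of the study and once more at 6 to 12 months (section 1.7.2), to at most 12 staff (section 1.7.4). A change of wording after the first round would leave the two rounds asking different questions.

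**Working it through.** Phase 3 states no calculated figure, so there is none to reproduce. The check sets the stated scope beside the survey text.

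1. **What phase 3 is about.** Sections 1.4.3, 1.7 and 1.7.2.2 all name multi-parametric ultrasound, the last two alongside micro ultrasound. Section 1.4.3.1 trains staff in multi-parametric techniques, and section 1.9.3 has them perform and score multi-parametric examinations.

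2. **What multi-parametric means.** Section 1.1.2 lists three components: standard frequency, Doppler and high frequency. Micro-ultrasound is the third.

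3. **What the survey names.** Micro-ultrasound appears in the subject sentence, in the main-role question, in all three role options, and in the descriptions of Parts B and C. Standard-frequency and Doppler imaging appear in none of these places. Coverage is 1 of 3 components.

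4. **Could the terms be interchangeable?** Sections 1.7 and 1.7.2.2 join the two with *and*, so the protocol treats them as different things. Section 1.1.2 makes one a part of the other.

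5. **Could the unseen items widen the scope?** The text at hand stops after Part A, Question 1, so the Part B and C items cannot be read. The introduction nevertheless states what both parts are about. Items on other techniques would contradict that description, so the wording would need correcting in either case.

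6. **Confidence and themes.** Sections 1.7.2.1 and 1.7.2.2 describe the content as familiarity, present and future normality, and the four theory domains. Appendix 8 describes Part C as statements to agree or disagree with, with a further option for statements that are not relevant, and tells respondents to tick a box. None of these descriptions mentions confidence or open text. Section 1.7.9, however, says that the survey questions are in Appendix 8, and nearly all of them are missing from the text at hand. This step therefore yields a question for the sponsor and no finding of absence.

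7. **Size of the per-technique remedy.** Three Part B questions for three techniques make 3 × 3 = 9 questions instead of 3, which is 6 more per respondent per round. With at most 12 staff and two rounds, that is at most 6 × 12 × 2 = 144 extra answers in the whole study.

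**The case against.** The strongest defence is that an implementation survey should target what is new. Appendix 8 is titled as a survey on new technology, section 1.7.2.1 asks about the new technology, and section 1.4.1 applies that description to the 29 MHz probe. These sonographers already use standard transrectal ultrasound. A micro-ultrasound focus would be a legitimate design choice.

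That stands as a reason why the sponsor might narrow phase 3. It does not reconcile the present text. Section 1.1.3 says that traditional ultrasound only guides where samples are taken, and section 1.1.4 treats diagnostic multi-parametric assessment as an additional skill for sonographers to develop. In the protocol's own account, then, diagnostic use of the whole technique is new. If the narrower focus is intended, the phase 3 aim should say so.

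It can also be said that little depends on this. Phase 3 serves a secondary objective (the last in section 1.3.2), section 1.7.3 rules out quantitative analysis, and patient data are untouched. That is correct and limits the weight of the point.

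A reader might go further and infer that the survey cannot deliver the phase 3 outcomes at all: that confidence would have no data and that themes would have to be drawn from tick-box counts. The documents do not support this. The Part B and C items and the format of the not-relevant option are not visible, the instrument is described as adapted, and a tick-box instruction does not exclude comment boxes. Even as described, the survey can supply answers on micro-ultrasound within the theory framework, professional group, and the response frequencies of section 1.7.10.

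**Conclusion.** The mismatch of scope is established from visible text. As written, the survey supports conclusions about micro-ultrasound, one of the three components in the protocol's own definition, and not about multi-parametric ultrasound as a whole. The consequence is confined to the implementation objective and to at most 12 respondents. It is worth correcting because the correction is nearly free before baseline and impossible to make good afterwards.

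The conclusion assumes that the unseen Part B and C items follow the subject that Appendix 8 gives them. The points on confidence and open text remain open: the described parts mention neither, and only the full questionnaire can show whether either is missing.

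**What to change.** Before the baseline round, do one of the following:

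- Reword the Appendix 8 introduction, role options and Parts B and C to refer to multi-parametric ultrasound (standard, Doppler and micro-ultrasound).
- Keep the micro-ultrasound wording but repeat the three Part B questions for each technique, so that views on each can be told apart.
- If micro-ultrasound is the intended subject, restrict the phase 3 aim in sections 1.4.3, 1.7 and 1.7.2.2, and the conclusions drawn, to micro-ultrasound.

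If the baseline round has already been run with the present wording, only the third option keeps the two rounds comparable.

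As a secondary check, the sponsor should confirm that both rounds contain items on confidence in knowledge and skills (section 1.4.3.1) and an open-text source for the themes and barriers promised in section 1.7.11. Such items should be added only if they are not already there.

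The cost is an amended appendix and a slightly longer online form. The third option costs only a change to the protocol text.

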1.1.4 Skill mix

The advent of multi-parametric ultrasound may enable a diagnostic assessment of the prostate, both at the initial biopsy and during AS. This will be an additional skill the sonographer will be required to develop. The benefits of skill mix have been documented by various authors, most recently Field and Snaith (2013). However, the impact of role development on sonographers and their radiologist colleagues, which includes changes to roles, responsibilities and accountabilities, has not been previously investigated in any depth. A workforce review by Parker and Harrison (2015) identified that appropriate training in ultrasound is key to providing a safe diagnostic and interventional ultrasound service but what constitutes appropriate training is less well defined.

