1.9.3 Phase 3 consent

Phase 3 participants will be invited into the study to both undertake multi-parametric ultrasound imaging, and to provide a retrospective score of the saved images. Phase 3 participants will also be required to undertake 2 surveys to provide their views of the new technology using the NoMAD

survey. The requirements of the study will be fully explained in a leaflet prior to a face to face discussion where written consent will be obtained by the lead researcher. Care will be taken to ensure there is no conflict between the lead researchers research role and her clinical role to prevent coercion of team members participating in the study

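### The phase 3 survey's role item has no interpretation option that clearly fits sonographers and imposes one perspective, so a contrast between professions may partly reflect scanning versus reading

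*Protocol*

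**What the plan says.** Appendix 8 opens with a role item offering three options: managing micro-ultrasound, performing it, and interpreting it. The performing option is "I am, or will be, involved in performing micro-US and prostate imaging". The interpreting option is "I am, or will be, involved in the interpretation of micro-US as radiologist or at MDT". The survey recognises that "people may have more than one role", but asks for the one option that best describes the main role and then instructs: "please answer all the statements from the perspective of the role you specify". Profession is asked separately in Part A, Question 1 ("Please provide your professional background"), where sonographer is a category.

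Elsewhere, section 1.9.3 says phase 3 participants are invited "to both undertake multi-parametric ultrasound imaging, and to provide a retrospective score of the saved images". Section 1.1.4 says of diagnostic assessment with multi-parametric ultrasound: "This will be an additional skill the sonographer will be required to develop". Section 1.2 makes the impact of skill mix a secondary objective, and section 1.7.2.2 plans to look at differences between grades of staff and "between professional groups involved".

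**The concern.** The practice change under study is that sonographers move from guiding biopsies to assessing the prostate diagnostically. The role item places interpretation with radiologists or the multi-disciplinary team (MDT) meeting, and its performing option mentions neither interpreting nor scoring. A sonographer following the instructions would most naturally choose performing and answer everything from there. Radiologists fit the interpretation option by name, and urologists fit it through the MDT.

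If that happens, a more negative set of answers from one profession could be read as a professional difference when it reflects the task the respondent had in mind. The skill-mix question is where that distinction matters.

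**Working it through.** The protocol states no figure on this point and none needs recomputing. The check sets the survey wording beside the phase 3 tasks and the planned comparison.

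1. **Do sonographers interpret in this study?** Yes. Section 1.1.3 describes them as trained and qualified to interpret ultrasound. Section 1.7.4 includes them among staff who both produce and interpret prostate imaging. Section 1.4.3.1 has participants score examinations regularly, and section 1.9.3 gives participants both tasks.

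2. **Which role option fits each profession?**
   - Radiologist: the interpretation option fits by name. Performing may also fit, since section 1.9.3 has participants scan as well as score.
   - Urologist: the interpretation option fits through the MDT, which is where section 1.7.4 places urologists' reading of imaging.
   - Sonographer: performing fits. Interpretation fits only if the sonographer reads at MDT, which the protocol neither states nor excludes.

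3. **Can a respondent give two perspectives?** Not under the instruction as written, which has one role govern all statements. Part C's route for statements that are not relevant lets a respondent opt out of a statement, but does not add a second perspective.

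4. **Is interpretation still asked about?** Yes. Section 1.7.2.1 has the survey ask phase 3 participants, with no limit by profession, how familiar using and interpreting or scoring the technology feels. It also asks whether the technology and its interpretation are, or will become, a normal part of their work.

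5. **Could role and profession be separated afterwards?** They are recorded as two items, so their overlap can be seen. Section 1.7.4 caps the group at 12, section 1.7.3 rules out quantitative analysis, and sections 1.7.10 and 1.7.11 plan frequency tables and a narrative. Three roles by five named professions gives 3 × 5 = 15 cells for at most 12 people, so adjustment is not realistic.

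6. **Who is eligible?** Section 1.7.4 includes urology consultants and registrars, and Question 1 lists them, but the inclusion criteria in section 1.7.7 name only radiologists and sonographers. If section 1.7.7 governs, two professions remain and the interpretation option names one of them, so the overlap of role with profession would be closer.

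Parts B and C are described in Appendix 8, but their items are not in the text at hand, nor is anything in Part A beyond Question 1. No conclusion is drawn from that.

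**The case against.** A reader might infer three stronger things, and the documents support none of them.

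- *Sonographers cannot answer as interpreters.* No rule bars a sonographer from the third option, which includes reading at MDT, and the item asks only for the best-fitting main role. The wording steers; it does not exclude.
- *Sonographers' views on interpretation are not collected.* Section 1.7.2.1 has the survey ask all phase 3 participants about interpreting and scoring. What may change is the role from which a sonographer answers.
- *The comparison between professions is confounded in a statistical sense.* Profession is recorded separately, radiologists who also scan may choose performing, and no estimate or test is planned.

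It can also be said that some overlap of role with profession simply reflects how the work is divided, and that the survey's stated repeat use is to detect change in perceptions over time (section 1.7.2), to which no harm is shown. Both points are fair.

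The mismatch in wording still stands. The survey acknowledges multiple roles and then allows one, and the option naming interpretation omits the profession whose interpretation is the subject of the study. A narrative contrast can be attributed to the wrong cause as readily as a numerical one, and with so few respondents the instrument is the practical place to prevent it.

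**Conclusion.** The point holds as a minor defect in a fixed instrument. The role item steers sonographers to answer as performers, so role and profession will tend to coincide, and a descriptive difference between professional groups may partly reflect scanning versus reading.

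This assumes that sonographers follow the instruction and mostly choose performing, which is likely but not certain. The number affected cannot be given: the protocol sets a maximum of 12 staff but no split by profession, so any percentage would rest on a guess. No patient outcome and no phase 1 or phase 2 analysis is affected.

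**What to change.** Make these changes before the baseline survey. The same tool is repeated at 6 to 12 months (sections 1.4.3.1 and 1.7.2), and a change between rounds would weaken the before-and-after reading.

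- Widen the third role option to interpretation or scoring of micro-ultrasound, and replace its closing qualifier with: as sonographer, radiologist, urologist or at MDT.
- Let respondents tick every role that applies, and ask them to answer from all the roles ticked.
- When narrating differences between professions, state the roles that respondents held.

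Two further steps are not advised. Completing Part C separately for each role would add burden and enter some people twice in a table of at most 12. Publishing role-by-profession cells could identify staff, in a group where sections 1.7.5 and 1.7.9 already say anonymity is hard to keep.

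The cost is a wording change in an online survey. The downside is slight: staff with two roles will give answers that are less tied to a single perspective.
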